4.3 VCP exposure, compliance

The following parameters of VCP administrations will be documented:

- Name and batch number(s)
- Dates and times of injections
- Doses in IU and IU/kg
- Purpose of injection (treatment of BE, prophylaxis of recurrent bleeding, surgery, prophylaxis after surgery and other on-demand treatment)

Overall descriptive summaries will be provided for

- Number of Injections
- Number of Exposure Days
- Total Dose (IU)
- Dose (IU/kg)
- Dose (IU/kg) per exposure day
- Reason for Administration
- Overall period of exposure (from first- to last dose of VCP)

All VCP treatment details will be listed for the FAS population.

4.4 Medical history

Medical history will be coded according to the Medical Dictionary for Regulatory Activities (MedDRA). Codes will be reviewed by a Medical Expert and approved before data base lock. Data on medical history will be summarized by MedDRA SOC and PT.

4.5 Prior and concomitant medication

Any relevant medication taken at time of screening and all new medications taken by the subject during the study period are defined as 'Concomitant'. Any changes of medications during the study period will also be recorded.

Concomitant medications will be coded using the WHO Drug Global thesaurus in the version current at the time of study start. Coding will be performed by the CRO and agreed upon with the sponsor before data base lock. (cf. DMP). Concomitant medication tables will show the frequencies of subjects by WHO Drug Global preferred term.

All details of concomitant medications will also be listed including the route, dose, frequency, start and stop date and indication.

Statistical Analysis Plan	Version 3.0		Page 11 of 17
Sponsor	Octapharma	Protocol No	WIL-29

4.6 Concomitant non-pharmacological measures, pre-medication

Not applicable.

4.7 Efficacy

The analysis of the efficacy of on-demand treatment with VCP will be based on the FAS and additionally on the PP set if these populations differ by >5%.

Primarily, all obtained data on treatment characteristics (VCP dosages, frequencies, total consumption) and BEs (site, type, duration, frequency, efficacy assessment) will be described by providing summary statistics.

For the efficacy analysis on bleeding episodes by site of bleeding a separate site category for 'Nose' will be generated. Assignment to this category will be based on the collected verbatim for 'Other site, specify' (e.g. Nose bleed, Epistaxis or similar meaning).

Bleeding episodes that are ongoing at screening visit but started prior to screening will be captured in study database and will be listed, but will be excluded from efficacy analysis.

4.7.1 Primary Endpoint

Primary endpoint of this study is to estimate the total annualized bleeding rate (TABR) during on-demand treatment with any VCP.

TABR will be calculated as the total number of spontaneous bleeds, traumatic bleeds and other bleeds in the time period between screening visit and the study completion visit, divided by the duration (in years) between first dose of VCP and the study completion visit. Surgery periods, and BEs occurring within these surgery periods, will be excluded from the calculation of TABR. Menstrual bleeds will not be included in this calculation, but reported and analyzed separately.

Descriptive statistics for TABR along with exploratory 95% Confidence Intervals will be presented.

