### **8.2 STUDY ENDPOINTS**

#### **8.2.1 Primary Endpoint**

The primary endpoint of this NIS is to characterise the total annualised bleeding rate (TABR) of patients with type 3, type 2 (except 2N), or severe type 1 VWD undergoing routine on-demand treatment with a VWF-containing product.

The TABR will be calculated as the total number of spontaneous, traumatic and other BEs in the time period between the start of data collection for each patient and the Study Completion Visit, divided by the duration (in years) between the start of data collection and the Study Completion Visit. Surgery periods, and BEs occurring within these surgery periods, as well as menstrual bleeds will be excluded from the calculation of TABR.

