#### 8.4.5 Patient Diaries

Documenting treatment and bleeding data is an integral part of home treatment for VWD. In this study, enrolled patients will be provided with a patient diary during the Screening Visit. Patients will be asked to complete their diaries and to bring them along to each follow-up visit. The completed diary pages will be collected by the treating physician, and the information recorded will be transcribed to the electronic Case Report Forms (eCRFs). The patient diaries are considered source data, and the original diary pages will be included in the patient's medical record.

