### 8.5.3 Bleeding Episode (BE) Data

Study participants will be instructed by the investigator on recording BEs in their patient diaries. For any BE occurring during the study, whether treated or not, the following data will be recorded:

- BE type (spontaneous, traumatic, postoperative, menstrual, other)
- BE site
- BE severity (minor, major) (see **Table 4**)
- Date and time the BE first occurred or was first noticed
- Date and time the BE ended
- BE treated or not treated
- Data on the administration of the VWF-containing product (see **Section 8.5.4**)
- Assessment of the effectiveness of treatment at the end of the BE (see **Section 8.5.5**)

All of these parameters will be documented by the patient (together with the treating physician in case of on-site treatments) in the patient diary. Patients who experience a major BE should be treated at the treatment centre, if possible.

Based on these data, the frequency of BEs and the TABR and SABR under on-demand treatment will be calculated.

If the treatment of a BE in one bleeding site is interrupted for more than 48 hours, two separate BEs will have to be recorded; if, in addition to the original bleeding site, another bleeding site is affected, these events will be recorded as separate BEs at any time.

The severity of menstrual bleeding will be categorized as either 'minor' or 'major'. Thus menstrual bleeding of regular intensity classified as minor will be considered normal. Heavy menstrual bleeding will be regarded as a BE of 'major' severity (see **Table 4**).

BE severity will be assessed using the criteria given in **Table 4**.

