4.1.2 Missing data

No imputations for missing data will be performed. Calculations pertaining to the derivation of annualized bleeding rates will be based on documented time periods only.

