6 DERIVATIONS AND TRANSFORMATIONS

6.1 Formulas for derived variables

Variable	Description
Durations between two dates	Later date minus earlier date plus 1, expressed in days. (Remark: Duration will be 1, if both dates are the same.)
Surgery Period	(Date of surgery – date of last VCP treatment for surgery + 1)/365.25
Total Annualized Bleeding Rate (TABR)	Number of bleedings excluding menstrual bleedings / (date of study completion – date of screening + 1)/365.25 (Surgery periods, and BEs occurring within these surgery periods, will be excluded from the calculation of TABR. BEs occurring at day of surgery but prior to start of surgery/start of treatment for surgery will be included into calculation)
Spontaneous Annualized Bleeding Rate (SABR)	Number of spontaneous bleedings / (date of study completion – date of screening + 1)/365.25 (Surgery periods, and BEs occurring within these surgery periods, will be excluded from the calculation of SABR. BEs occurring at day of surgery but prior to start of surgery/start of treatment for surgery will be included into calculation)
Traumatic Annualized Bleeding Rate (TRABR)	Number of spontaneous bleedings / (date of study completion – date of screening + 1)/365.25 (Surgery periods, and BEs occurring within these surgery periods, will be excluded from the calculation of TRABR. BEs occurring at day of surgery but prior to start of surgery/start of treatment for surgery will be included into calculation)
Heavy Menstrual Bleeding Rate (HMBR)	Number of heavy menstrual bleedings* / (date of study completion – date of screening + 1)/365.25 (* for a definition refer to section 6.4)
ED	Exposure day = each calendar day the subject received VCP

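### SAP 4.7.1 counts bleeds from screening but divides by time from the first VCP dose, which contradicts SAP 6.1 and the protocol and inflates the primary TABR

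*SAP*

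**What the plan says.** The documents define the primary rate in three places, and the denominators do not agree.

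- **Protocol 8.2.1** uses one window. Bleeds are counted "in the time period between the start of data collection for each patient and the Study Completion Visit", and the count is "divided by the duration (in years) between the start of data collection and the Study Completion Visit".
- **SAP 4.7.1** uses two. Bleeds are counted "in the time period between screening visit and the study completion visit", but the count is "divided by the duration (in years) between first dose of VCP and the study completion visit".
- **SAP 6.1** returns to screening: "Number of bleedings excluding menstrual bleedings / (date of study completion – date of screening + 1)/365.25".

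SAP 4.1.2 adds that "Calculations pertaining to the derivation of annualized bleeding rates will be based on documented time periods only". No term in the 6.1 formula does this.

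SAP 2.2, which lists statistical deviations from the protocol, covers only the definition of surgery periods for bleeding rates. A new starting point for the denominator is not mentioned. SABR and TRABR (SAP 4.7.2) and the heavy menstrual bleeding rate (SAP 4.7.4) are all defined by analogy with TABR, so they inherit the conflict.

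**The concern.** A rate needs its events and its time at risk from the same window. Bleed recording starts at screening: "enrolled patients will be provided with a patient diary during the Screening Visit" (Protocol 8.4.5). Untreated bleeds count as well: "For any BE occurring during the study, whether treated or not, the following data will be recorded" (Protocol 8.5.3). In on-demand care the first on-study dose is normally given because a bleed has happened. Starting the clock at that dose removes the bleed-free stretch before it, while any untreated bleeds in that stretch stay in the numerator.

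A patient who needs no VCP during follow-up has no 4.7.1 denominator, although SAP 3.1 places every enrolled subject in the full analysis set. Such patients are likely to be among the lowest bleeders, so losing them pushes the mean up further.

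Protocol 6.2 says the data will serve for historical comparison with a study of prophylaxis. An on-demand rate that is too high would exaggerate any apparent benefit of prophylaxis. The study is descriptive, but the rate itself is what it delivers.

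**Working it through.** **The plan's own figure.** Protocol 8.8 and SAP 1.4 give a 95% confidence half-width of ±0.8 for n = 55 and SD = 3. Check: 1.96 × 3/√55 = 0.793, which agrees. It serves below as a yardstick.

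**Inputs.** Follow-up is around 6 months (Protocol 8.4.2); I take T = 183 days. The documents give no time to first dose, bleeding rate, share of bleeds treated or between-patient variation. Those values are assumptions, shown as a range.

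**One patient.** Count the screening day as day 1 and let the first dose fall on day k. For N bleeds:

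- SAP 6.1 (intended reading): N / (T/365.25)
- SAP 4.7.1: N / ((T − k + 1)/365.25)
- Ratio: T/(T − k + 1), above 1 whenever the first dose comes after the screening day

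With N = 3 and k = 60, 6.1 gives 3/(183/365.25) = 5.99 per year. SAP 4.7.1 gives 3/(124/365.25) = 8.84 per year. The ratio is 183/124 = 1.48.

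For 5 bleeds in 183 days, 6.1 gives 9.98 per year. With d days from screening to first dose, 4.7.1 gives:

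| d (days) | Factor 183/(183 − d) | 4.7.1 rate per year |
|---|---|---|
| 14 | 1.08 | 10.81 |
| 30 | 1.20 | 11.94 |
| 60 | 1.49 | 14.85 |
| 90 | 1.97 | 19.64 |
| no dose | – | undefined |

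**A cohort.** I simulated 183 days with bleeds uniform in time and the first treated bleed taken as the first dose. Counts were Poisson, or gamma-Poisson where between-patient CV is 0.7. Each scenario had 40,000 patients, and repeat runs move the last two rows by a few tenths.

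| True mean per year | Bleeds treated | CV | No dose | 6.1 mean, dosed patients only | 4.7.1 mean |
|---|---|---|---|---|---|
| 20 | all | 0 | 0% | 20.0 | 22.2 |
| 10 | all | 0 | 0.7% | 10.1 | 12.9 |
| 4.5 | all | 0 | about 10.5% | 5.0 | 9.9 |
| 20 | 60% | 0.7 | about 6% | 21.1 | 27.3 |
| 10 | 60% | 0.7 | about 16% | 11.6 | 20.2 |

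The undosed share in the third row can be checked by hand: exp(−4.5 × 183/365.25) = exp(−2.25) = 10.5%.

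The last two columns compare the same patients, so their gap is the denominator effect alone: +11%, +28%, about double, +29% and +74%. The rise from the true mean to the fifth column is the effect of losing undosed patients.

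Medians among dosed patients also rise: 20.0 to 22.0 (first row), 10.0 to 12.2 (second row) and 10.0 to 14.7 (last row).

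**Against the yardstick.** The smallest shift, 22.2 − 20.0 = 2.2 per year, is 2.2/0.793 = 2.8 times the half-width the plan quotes.

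**The case against.** The strongest reply is that 6.1 is the derivation section and will be programmed, in which case no bias arises. That condition is real, but nothing in the SAP says 6.1 prevails. The sentence in SAP section 4 on how listed derived data such as TABR are calculated shows no section number in the public text. Nor is 6.1 clean enough to win by default: its TRABR formula counts spontaneous bleeds, and its TABR expression, read left to right, divides by 365.25 a second time.

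Several other points stand in part:

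- **Likely size.** Protocol 8.5.2 prefers patients with at least 5 treated spontaneous bleeds in 3 months, about 5 × 4 = 20 per year. With every bleed treated, that is where the inflation is smallest (+11%). The same section lets the investigator admit less frequent bleeders, for whom it is larger.
- **Means driven by the tail.** First doses late in follow-up give extreme rates. The SAP also reports medians and quartiles, which move less but in the same direction.
- **Undosed patients.** The SAP does not say they are dropped. It leaves their rate undefined and gives no rule for handling it.
- **SAP 4.1.2.** The documented-time rule is compatible with either starting point. The gap is that 6.1 does not carry it out.
- **Another reading.** If the first dose meant one given before the study, the rate would be too low instead. That reading is less natural, and the two windows would still not match.
- **The comparison.** The analysis against the prophylaxis study is not in these documents, so its distortion can be given in direction but not in size.

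**Conclusion.** The concern holds. The definition of the primary endpoint in SAP 4.7.1 is internally mismatched, contradicts SAP 6.1 and Protocol 8.2.1, and is not declared as a deviation. Programmed as written, with the first dose read as the first on-study dose, it raises TABR for every patient whose first dose comes after the screening day. It also leaves undosed patients without a rate.

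Under the assumptions above, the mean rises by about 11% for frequent bleeders whose every bleed is treated, and roughly doubles at 4.5 per year. The size in this cohort depends on time to first dose, which the documents do not give; the direction does not. The contradiction should be resolved before the primary endpoint is programmed.

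**What to change.** 1. In SAP 4.7.1, run the denominator from the screening visit to the study completion visit, or to the last documented diary date if earlier, minus surgery periods and undocumented periods. The diary cut-off is my way of carrying out SAP 4.1.2.
2. Write the same denominator into SAP 6.1 for TABR, SABR, TRABR and HMBR, with brackets that make the conversion to years unambiguous.
3. State that patients with no VCP dose stay in the analysis with their observed time, so a patient with no bleeds contributes a rate of zero.
4. State that 6.1 governs the derivation of bleeding rates, and complete the cross-reference in SAP section 4.

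The cost is SAP wording and the matching program code. Screening, completion, surgery and diary dates are already collected, so no new data are needed.

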4.7.2 Secondary Endpoints

Secondary endpoints are:

- Spontaneous annualized bleeding rate (SABR), calculated in analogy with TABR
- Data on the consumption of VCP product (VWF/FVIII IU/kg per month per patient) used for routine on-demand treatment

The following secondary efficacy endpoints will be studied except in Croatian centers:

- Effectiveness of VCP in the treatment of BEs based on the proportion of successfully treated BEs (definition see section 6.2)
- Effectiveness of surgical prophylaxis with VCP based on the proportion of successfully treated surgeries (definition see section 6.3)
- Pictorial Blood Loss Assessment Chart (PBAC) score

Regarding the VCP administration data, the following parameters will be documented:

- Dates and times of VCP injections
- Doses of VCP in IU and IU/kg and VCP batch numbers
- Reason for VCP injection (prophylaxis, treatment of BE, surgery)

Statistical Analysis Plan	Version 3.0		Page 12 of 17
Sponsor	Octapharma	Protocol No	WIL-29

Descriptive statistics will also be presented for the SABR and for time in study, exposure days, number of infusions and dosages of VCP overall and by reason for VCP injection.

Additionally, descriptive statistics will be presented for the traumatic annualized bleeding rate (TRABR), calculated in analogy with TABR.

4.7.3 Efficacy in surgical prophylaxis

The assessments will be performed only in non-Croatian centres.

Efficacy in surgical prophylaxis will be analyzed descriptively, presenting summary tables and listings on all aspects of surgical treatment and procedures as well as efficacy ratings.

The following surgery-related parameters will be presented:

- Location, severity (minor or major, for definitions see protocol) and type (planned or emergency) of surgery
- Actual duration of surgical procedure
- Actual blood loss
- Pre-, intra-, and/or postoperative VCP administration data (only listed)
- Pre-, intra-, and postoperative FVIII and VWF & c plasma levels (only listed)
- Details on concomitantly administered products, except standard anesthetic products (only listed)
- Blood transfusion requirements (only listed)
- Assessment of efficacy of surgical prophylaxis at end of postoperative period by treating physician
- Number of successfully treated surgeries ('excellent' or 'good' overall efficacy rating)

Procedures that meet the following criteria are considered as 'major' surgeries. All other procedures are considered 'minor'

- General or spinal anaesthesia required
- Operating into the great body cavities required
- Severe haemorrhage during surgery possible
- Haemostatic therapy for at least 6 days required
- Orthopaedic interventions involving joints (ankle, knee, hip, wrist, elbow, shoulder)
- 3rd molar extraction or extraction of ≥ 3 teeth
- Surgeries/conditions in which the patient's life is at stake

For descriptive statistics on VCP consumption in context of surgeries by time point, all administrations documented under reason for treatment "Surgery" which have been administered before start of surgery will be considered as preoperative and administered between start and end of surgery as intraoperative treatments. Post-operative treatments will include all VCP treatments documented under reason for treatment "Prophylaxis after surgery".

Statistical Analysis Plan	Version 3.0		Page 13 of 17
Sponsor	Octapharma	Protocol No	WIL-29

4.7.4 Menstrual Bleedings (only female patients of childbearing potential)

For female patients, the results of the PBAC score over time will be summarized in descriptive tables for each complete menstrual cycle including changes to baseline.

Annualized rates of heavy menstrual bleedings will be calculated in analogy with TABR and summarized in descriptive tables. For the exploratory endpoint 'Annualized rate of heavy menstrual bleeds' descriptive statistics will be tabulated.

4.8 Safety

All safety analyses will be based on the FAS population.

The analysis of safety will include the occurrence of Adverse Drug Reactions and the occurrence of VWF/FVIII inhibitors.

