3 ANALYSIS POPULATIONS

The disposition of patients will be displayed according to the following analysis populations:

- Full Analysis set (FAS)
- Per-Protocol (PP) set
- Surgery (SURG) set

Membership of subjects will be decided upon in a DRM with the Sponsor before database lock. The proper flags for analysis sets exclusion (e.g., exclusion from PP set), will be included in the analysis dataset. The protocol deviation list should be finalized before database lock.

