3.1 Full Analysis Set

The **full analysis (FAS) set** defined according to the intention-to-treat (ITT) principle will include all enrolled subjects.

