3.3 Surgery Set

The **surgery (SURG) set** will be a subset of the FAS, containing all subjects who underwent a surgical procedure treated with any VCP prior to start of surgery.

Statistical Analysis Plan	Version 3.0		Page 8 of 17
Sponsor	Octapharma	Protocol No	WIL-29

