4 STATISTICAL ANALYSES

All statistical analyses will be performed using the SAS® software (Version 9.4 or later).

Descriptive statistics will always be given for the entire population.

The analysis of safety will be based on the FAS set.

Analysis of the primary endpoint will be performed on the FAS and PP set.

For secondary endpoints (except endpoints regarding surgeries), FAS and PP analyses will be carried out, unless these analysis sets differ by no more than 5% of patients in the FAS.

Analysis of the efficacy and safety of VCP in surgeries will be based on the SURG set.

If not stated otherwise, the following standard descriptive statistics will be presented:

Descriptive statistics for continuous data

Number of subjects (N), arithmetic mean, standard deviation (SD), minimum, lower quartile, median, upper quartile and maximum will be presented. These descriptive statistics will be determined for measured values and where applicable for differences to baseline.

Descriptive statistics for categorical data

Absolute frequencies (N) will be presented with 0, relative frequencies (%) with 1 decimal. For changes from baseline, shift tables may be generated.

Inferential statistics

Confirmatory statistical inferences are not planned. Any statistical inferences (e.g. confidence intervals) will be of exploratory nature.

All p-values will be rounded to 4 decimals (p<0.0001 will be displayed, if the p-values are less than 0.0001). Unless otherwise specified, statistical significance will be declared if the rounded p-value will be less than 0.05.

All confidence intervals (CI) will be derived two-sided and at a confidence probability of $1-\alpha = 0.95$.

Statistical Analysis Plan	Version 3.0		Page 9 of 17
Sponsor	Octapharma	Protocol No	WIL-29

Listings

All subject data will be listed by subject. Identification variable will be the subject ID (composed of study, center and subject number separated by a hyphen, e.g. '29-01-01'. Any derived data, e.g. TABR, listed will also be stored permanently and will be calculated as outlined in section of this SAP.

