4.8.1 Adverse Drug Reactions

Any adverse event (AE) which has a reasonable possibility of a causal relationship with the medicinal product will be considered as an Adverse Drug Reaction (ADR).

Adverse Drug Reactions (ADRs) will be coded by the Data Management of the CRO according to version stated in the DMP. Coding will be agreed upon with the Sponsor before database lock (cf. DMP).

All ADRs occurring after first VCP administration will be listed in appendix 16.2 of the report.

The analysis will include only treatment-emergent ADRs (TEADRs), i.e. all documented ADRs that started or worsened after the start of VCP infusion. It is assumed that for each increase in intensity of an ADR a new entry of the ADR will be done by the investigator; hence such cases will be analyzed like different phases of the same ADR.

A descriptive analysis will be performed. Incidences will be presented by primary system organ classes (SOC) and incidences of PT within primary SOC sorted according to the Internationally Agreed Order.

Multiple counts within a PT or SOC (repeated or different included terms or changes in descriptors) will be counted only once for the calculation of incidences.

Global incidences will be calculated for:

- All TEADRs irrespective of the causality assessment
- TEADRs by worst severity

A listing of "special cases" containing subject identification, age, sex, ADR descriptors, start and end of treatment will be prepared for the following types of TEADRs:

- Serious ADRs (SADRs)
- ADRs which led to death
- ADRs which led to discontinuation

Serious non-treatment emergent ADRs will be listed separately.

Statistical Analysis Plan	Version 3.0		Page 14 of 17
Sponsor	Octapharma	Protocol No	WIL-29

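### ADR incidences are to be computed on all enrolled patients, so any patient with no on-study dose of a VWF-containing product lowers the reported figure

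*SAP*

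**What the plan says.** The population for safety is given twice in the SAP. Section 4 states "The analysis of safety will be based on the FAS set", and Section 4.8 states "All safety analyses will be based on the FAS population". Section 3.1 describes the FAS as "defined according to the intention-to-treat (ITT) principle will include all enrolled subjects", without requiring a dose.

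Section 4.8.1 restricts the ADR analysis to treatment-emergent ADRs (TEADRs), meaning "all documented ADRs that started or worsened after the start of VCP infusion". On the tables it says "Incidences will be presented by primary system organ classes (SOC) and incidences of PT within primary SOC", and each patient counts once per term.

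Section 3 lists three sets: FAS, PP and SURG. The only one that requires a dose is SURG, "containing all subjects who underwent a surgical procedure treated with any VCP prior to start of surgery". It covers surgical patients only. No safety or treated set is defined.

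**The concern.** The numerator of a TEADR incidence requires a VCP infusion and the denominator does not. In a trial where every patient is dosed on day 1 the distinction is empty. Here treatment is on demand, follow-up is about 6 months (Protocol 8.4.2), and bleeding episodes are recorded whether or not they are treated (Protocol 8.5.3). A patient can therefore complete the study with no on-study dose, cannot contribute a TEADR, and still counts in the denominator.

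The effect can go in one direction only, which is downward, towards a more reassuring result. Safety of the product is a named secondary objective (Protocol 7.2, SAP 1.2), so the denominator should match the patients at risk.

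**Working it through.** **Inputs from the documents**
- N = 55, SD of the annualised bleeding rate (ABR) 3 or less, 95% CI half-width ±0.8: SAP 1.4, Protocol 8.8.
- Follow-up about 0.5 years: Protocol 8.4.2.
- Preferred history of at least 5 treated spontaneous bleeds in 3 months, i.e. 5 × 4 = 20 a year: Protocol 8.5.2.

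Neither document gives an expected ADR incidence or an expected number of undosed patients.

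**Step 1: the plan's own figure.** 1.960 × 3/√55 = 0.793, which rounds to the stated 0.8. It reproduces.

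**Step 2: dilution for a given number undosed.** If x patients have a TEADR and u of the 55 are never dosed on study, the FAS incidence is x/55 and the incidence among dosed patients is x/(55 − u). Their ratio is (55 − u)/55. With x = 3 and u assumed:

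| u | FAS | Dosed patients | Ratio |
|---|---|---|---|
| 0 | 5.5% | 5.5% | 100% |
| 1 | 5.5% | 5.6% | 98.2% |
| 3 | 5.5% | 5.8% | 94.5% |
| 6 | 5.5% | 6.1% | 89.1% |

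If no TEADR is seen, the point estimate is 0% either way. The one-sided 95% upper bound, 1 − 0.05^(1/n), is 5.3% for n = 55 and 5.9% for n = 49.

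**Step 3: what u might be.** Assume Poisson bleeds at rate λ a year, every bleed treated, and no dosing for any other reason. Then P(no dose in 0.5 years) = exp(−0.5λ):

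| λ per year | P(no dose) | Expected undosed of 55 |
|---|---|---|
| 20 (preferred history) | 0.00005 | 0.0 |
| 10 (assumed) | 0.0067 | 0.4 |
| 6 (assumed) | 0.050 | 2.7 |
| 4.5 (from SD ≤ 3) | 0.105 | 5.8 |

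**Step 4: where 4.5 comes from.** An ABR from 6 months is twice the bleed count, and the count has mean 0.5λ. Under Poisson its variance is therefore 4 × 0.5λ = 2λ. SD ≤ 3 means 2λ ≤ 9, so λ ≤ 4.5. At λ = 4.5, exp(−2.25) = 10.5%, about 6 of 55.

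The 20-a-year and SD ≤ 3 scenarios cannot both hold under Poisson, since λ = 20 gives an SD of √40 = 6.3. The documents do not say which is nearer the truth, so both ends are shown.

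**The case against.** **Eligibility selects against undosed patients.** Protocol 8.3.2 asks for *frequent* on-demand treatment, 8.5.2 prefers a heavy recent history of treated bleeds, and 8.3.3 excludes women treated only once a month for menstrual bleeding. This stands, and it makes undosed patients less likely. It does not exclude them: *frequent* carries no number, and the preferred history can be set aside on the investigator's judgement.

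**No counted bleed is not the same as no dose.** ABR leaves out menstrual bleeds and surgery periods, either of which may lead to dosing, and SAP 4.3 lists further reasons for injection. These lower the undosed share. ABR also counts untreated bleeds, which raises it. So the 10% is an illustration under stated assumptions, not an estimate.

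**Larger figures do not follow.** A reader might add between-patient variation at a mean of 4.5 and arrive at 22% to 31% undosed (gamma shape 2 and 1). The documents do not support that. The variance becomes 2λ + λ²/k, which gives an SD of 4.4 (k = 2) or 5.4 (k = 1) and breaks the SD ≤ 3 assumption that produced 4.5. Holding the SD at 3 instead gives larger shares with no counted bleed (36% and 48%), but only at means of 2.7 and 2.2 a year, far below the preferred history.

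**The information is available elsewhere.** Injections and exposure days are summarised, VCP treatment is listed, and outputs show N and a contributing n. A reader could rebuild the denominator. However, n is not defined as patients dosed, and the incidence tables would still carry the diluted percentage.

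**The consequence is small.** The analysis is descriptive. For 3 of 55 the exact 95% CI is 1.1% to 15.1%, much wider than a shift from 5.5% to 6.1%. That is fair.

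**Conclusion.** The mismatch is explicit in the SAP: TEADR incidences require an infusion, their denominator does not, and no defined set corrects this. Any undosed FAS patient lowers the reported incidence by the factor (55 − u)/55.

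A reader might infer that the incidence is certain to be biased low. The documents do not support that, because the bias exists only if at least one enrolled patient has no on-study dose, and they give no such number. On the assumptions shown the effect runs from negligible (20 treated bleeds a year) to a relative understatement of about 10% (mean ABR 4.5, Poisson counts, all counted bleeds treated, no other dosing).

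Nor does the point reach every safety output. Inhibitors, pregnancies and the other safety information can arise in previously treated patients who are not dosed on study, and the FAS is reasonable for those. Only the TEADR percentages need a different denominator. It is a modest point, worth correcting because the correction is nearly free.

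**What to change.** - In SAP 3, add a safety set: FAS patients with at least one VCP administration between screening and study completion.
- In SAP 4.8.1, make it the denominator for TEADR incidences, and adjust the general statements in SAP 4 and 4.8 to match.
- Report how many FAS patients were not dosed on study.
- Optionally, add TEADRs per exposure day; SAP 6.1 already derives exposure days.
- Keep inhibitors, pregnancies and the other safety listings on the FAS.

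The cost is some SAP wording and one flag, which can be set with the other analysis-set flags before database lock. If every patient is dosed, no percentage changes. If not, the reported incidence becomes slightly less favourable.
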